Vitamin D serum level was measures using the ELISA technique. The Cal Biotech Vitamin D Kit (Mannheim, Germany) was used, which is a solid phase enzyme linked immunoassay (ELISA), based on the principal of competitive binding. Vitamin D deficiency was defined as serum Vit. D below 20 ng/ml.

Sensitivity:

The sensitivity of this test kit is 0.67ng/ml. Sensitivity was determined by calculating the mean plus 2SD of the standard zero point tested 20 times in the same Statistical Methods run.

Statistical methods

The collected data were coded, tabulated, and statistically analyzed using IBM SPSS statistics (Statistical Package for Social Sciences) software version 28.0, IBM Corp., Chicago, USA, 2021. Quantitative data tested for normality using Shapiro-Wilk test, then described as mean \pm SD (standard deviation), and then compared using independent t-test. Qualitative data described as number and percentage and compared using Chi square test. Pearson test was used for correlations. ROC curve was used to evaluate the performance of variables to differentiate between conditions. The level of significance was taken at p-value <0.050 was significant, otherwise was non-significant.

Diagnostic characteristics was calculated as follows:

- Sensitivity = (True positive test / Total positive golden) x 100
- Specificity = (True negative test / Total negative golden) x 100
- Diagnostic accuracy = ([True positive test + True negative test] / Total cases) x 100
- Youden's index = sensitivity + specificity - 1
- Predictive positive value = (True positive test / Total positive test) x 100
- Predictive negative value = (True negative test / Total negative test) x 100
- Likelihood ratio positive (LR+) = (sensitivity / 1-specificity)
- Likelihood ratio negative (LR-) = (1- sensitivity / specificity)

Diagnostic odds ratio (DOR)= LR+/ LR-

Serum level of vitamin D, in monosymptomatic enuretic children and non-enuretic children: a comparative study

[name] [name]*, [name]. [name]*, [name] **, [name]*.

* Urology Department, Faculty of Medicine, Ain Shams University

** Damanhour National Medical Institute.

Corresponding Author:

[name] [name]

Associate professor of urology

Faculty of Medicine

Ain shams university

Email: [contact]

[contact]

[name], Faculty of medicine, El Demerdash hospital.

[name]

[contact]

Professor and chief of urology department

Faculty of medicine

Ain Shams university

[name]

[contact]

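### Youden's index, LR+ and LR- combine a bare 1 with sensitivity and specificity defined as percentages, and LR+ and LR- also lack inner brackets, so the printed rules do not give the named measures

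*Combined protocol and SAP*

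**What the plan says.** The relevant text is the list of diagnostic measures at the end of the Statistical methods section. It is introduced as the calculation rule: "Diagnostic characteristics was calculated as follows".

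The two basic measures are put on a 0 to 100 scale:

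- "Sensitivity = (True positive test / Total positive golden) x 100"
- "Specificity = (True negative test / Total negative golden) x 100"

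Three derived measures then use those terms with a bare 1 (the closing bracket of each likelihood ratio falls just outside the quoted words):

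- Youden's "index = sensitivity + specificity - 1"
- "Likelihood ratio positive (LR+) = (sensitivity / 1-specificity"
- "Likelihood ratio negative (LR-) = (1- sensitivity / specificity"

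The odds ratio is the quotient of the two likelihood ratios: "Diagnostic odds ratio (DOR)= LR+/ LR" (followed by the minus sign of LR-).

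No sentence says that proportions are to be used in the derived measures. The document reports no value for any of these quantities.

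**The concern.** There are two separate faults.

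**Scale.** Subtracting from 1, or subtracting 1 from a sum, makes sense only when sensitivity and specificity are proportions. The list defines them as percentages.

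**Grouping.** In LR+ and LR- the only brackets enclose the whole right-hand side. By ordinary operator order, LR+ becomes (sensitivity / 1) minus specificity, and LR- becomes 1 minus (sensitivity / specificity). Neither is a likelihood ratio. The list does group a sum where one is needed, in "Diagnostic accuracy = ([True positive test + True negative test] / Total cases) x 100", so inner brackets are part of its own notation. Youden's index needs no brackets and has only the scale fault.

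At stake is whether someone who applies the stated rules would obtain the named measures. Most literal results would be visibly impossible. The case most likely to pass unnoticed is a partial repair, with brackets supplied and percentages still entered. That yields a positive odds ratio close to 1, which looks like a test with almost no discrimination.

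**Working it through.** **Inputs.** The formulas come from the Statistical methods list, and the group sizes of 60 cases and 60 controls from Patients and methods. The document gives no diagnostic results, so there is no figure to reproduce. The counts below are assumptions for illustration: 48 of 60 cases test positive (sensitivity 80%) and 42 of 60 controls test negative (specificity 70%). S and P denote sensitivity and specificity in percent; Se and Sp denote the same as proportions.

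**1. Standard formulas, proportions**

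- Youden = Se + Sp - 1 = 0.80 + 0.70 - 1 = 0.50
- LR+ = Se / (1 - Sp) = 0.80 / 0.30 = 2.67
- LR- = (1 - Se) / Sp = 0.20 / 0.70 = 0.29
- DOR = LR+ / LR- = 9.33; from the counts, (48 x 42) / (18 x 12) = 2016 / 216 = 9.33

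**2. Exactly as printed: percentages, ordinary operator order**

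- Youden = 80 + 70 - 1 = 149
- LR+ = 80 / 1 - 70 = 10
- LR- = 1 - 80 / 70 = -0.14
- DOR = 10 / (-0.1429) = -70

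The -70 does not depend on the example. In general DOR = (S - P) / (1 - S/P) = (S - P) / ((P - S)/P) = -P. The printed DOR is minus the specificity whatever the sensitivity, and 0/0 when the two are equal. The printed LR+ is negative when S is below P, and the printed LR- is negative when S is above P.

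**3. Brackets supplied, percentages kept**

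- Youden = 149, unchanged
- LR+ = 80 / (1 - 70) = 80 / (-69) = -1.16
- LR- = (1 - 80) / 70 = -79 / 70 = -1.13
- DOR = SP / ((S - 1)(P - 1)) = 5600 / (79 x 69) = 5600 / 5451 = 1.03

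**4. Proportions used, brackets still missing**

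- Youden = 0.50, correct
- LR+ = 0.80 - 0.70 = 0.10
- LR- = 1 - 0.80 / 0.70 = -0.14
- DOR = 0.10 / (-0.1429) = -0.70

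Changing the scale alone restores Youden's index. LR+, LR- and DOR need both changes. In the strictly literal LR- the ratio S/P has no scale, so there the missing bracket alone does the damage; the scale fault in LR- appears once the bracket is supplied.

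**5. Two further assumed pairs**

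| Sensitivity / specificity | Reading | Youden | LR+ | LR- | DOR |
|---|---|---|---|---|---|
| 60% / 80% | Correct | 0.40 | 3.0 | 0.50 | 6.0 |
| | As printed | 139 | -20 | 0.25 | -80 |
| | Brackets, percentages | 139 | -0.76 | -0.74 | 1.03 |
| 90% / 90% | Correct | 0.80 | 9.0 | 0.11 | 81 |
| | As printed | 179 | 0 | 0 | 0/0 |
| | Brackets, percentages | 179 | -1.01 | -0.99 | 1.02 |

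Across the three pairs the correct DOR runs from 6.0 to 81, while the version with brackets and percentages stays at 1.02 to 1.03. Because both of its likelihood ratios are negative, their quotient is positive, and looking at DOR alone would not reveal the error.

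**The case against.** The strongest reply is that this is shorthand rather than a method error. Every measure is named, each formula has the right terms in the usual order, and 80% can be read as 0.80, so that 80% + 70% - 1 is 0.50. A reader who knows the measures has no rival formula to choose. The work is described in the past tense and the data as analysed in SPSS, so the values may well have been obtained correctly. Results such as a Youden's index of 149 or an odds ratio of -70 would be expected to draw attention. The stated aim concerns the relationship between vitamin D deficiency and enuresis and the correlation with urine osmolality, and the comparisons and correlations that serve it do not use these formulas.

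Much of this stands. The intent is recognisable, no wrong value is shown, and the reach is narrow; these are reasons to rate the point minor. They do not make the printed rules correct. The list is offered as the way the measures were calculated. The document names SPSS for the analysis generally but does not say that the likelihood ratios or DOR came by another route. Nor would every misapplication be conspicuous: the version with brackets and percentages gives a believable DOR. Loss of brackets in text extraction is an unlikely explanation, since the outer brackets and those in the accuracy line survived, and the scale fault does not depend on brackets.

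**Conclusion.** The concern holds, as a minor error in the written formulas. Followed exactly, the list gives wrong values for Youden's index, LR+ and LR-, and for DOR through its inputs: 149, 10, -0.14 and -70, against 0.50, 2.67, 0.29 and 9.33 at the assumed 80% and 70%. The sizes depend on those assumed values. That the printed DOR equals minus the specificity does not depend on them, provided sensitivity and specificity differ.

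Whether any computed result was affected cannot be determined from the document. The t-test, chi-square, Pearson and ROC analyses are untouched, as are the formulas for sensitivity, specificity, accuracy and the predictive values.

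**What to change.** State that sensitivity and specificity enter the derived measures as proportions, with percentages used for display only, and write:

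- Youden's index = Se + Sp - 1
- LR+ = Se / (1 - Sp)
- LR- = (1 - Se) / Sp
- DOR = LR+ / LR- = (TP x TN) / (FP x FN)

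Then confirm that the values actually computed used these forms, checking the two likelihood ratios as well as DOR, and recompute only if they did not. The count form of DOR is a convenient cross-check because it involves no percentages.

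The cost is one sentence on scale, brackets in two lines and one check. No new data or analysis is needed.
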